Day	≤21 days prior to Visit C1 (D1)	D1	D2	D3 b	D8	D15	D1	D2	D3 b	D2°	-	30 days after last dose	60 days after last dose	-
Before BNT411 infusion (on infusion days) or on day of visit	E1		X,E3, U a	X,E3, U a	X,E3	X		X,E3, U a	X,(E3) ,U a	X,E3	X,E1	X,E1	X,E1	X,E1, U a
Start of infusion			Ud											
End of infusion (+ 5 min)			X,E3		X,E3			X,E3		X,E3				
Start of infusion + 1 hour (± 5 min)			X					(X)						
Start of infusion + 2.5 hours (± 10 min)			X		X			X		X				
Start of infusion + 4 hours (± 15 min)			X		X			X		X				
Start of infusion + 6 hours (± 15 min)			X,E3ª		X			X,E3 a,		(X)				
Start of infusion + 8 hours (± 15 min)			X					(X)						

Note: Time points for blood and urine sampling are to be followed as closely as possible but time deviations no longer than 2 hours will not be reported as protocol deviations as long as the exact times of sampling and dose are known.

E1 – Single electrocardiogram (ECG) assessment.

E3 – Triplicate ECG assessments.

- X Blood sampling
- U Urine sampling

UNS - Unscheduled visit

- (X) Blood sampling will only be performed in potential additional patients enrolled to expand the cohorts for RP2D confirmation.
- (E3) Triplicate ECG assessment will only be performed in potential additional patients enrolled to expand the cohorts for RP2D.
- a Sampling time and sample volume have to be documented.
- b Time window for the Day 3 sample in the dose escalation is 24 hours  $\pm$  1 hour after the start of infusion on Day 2.
- c PK and ECG must be obtained in Cycle 3, Cycle 5, Cycle 7, and every 4 cycles thereafter (i.e., Cycles 3, 5, 7, 11, 15, etc.)
- d 6-hour urine collection after start of BNT411 infusion and total volume collected should be documented.
- e After C3D1, PBMCs (for immune phenotyping and TCR profiling) will no longer be collected. Collection of PMBCs at treatment discontinuation and/or unscheduled visits is only required if the patient discontinues trial treatment prior to C3D1.

**Table 1-5:** Overview of Safety Reporting in Different Countries

Notes: If not specified otherwise, when AE is mentioned, it should also include SAE.

Country	Trial Phase				
	Screening	Treatment Phase	Safety Follow-up Phase	Survival Follow-up Phase	Beyond Trial Closure (if patient is alive and not lost to follow-up)

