Tumor FFPE sample	$X^1$								
Tumor biopsy	$X^2$						$X^2$	$X^2$	$X^2$
Blood compartment									
Cytokines					$X^3$			$X^3$	$X^3$
Immune Phenotyping		$X^4$		X 	X 	X 	$X^4$	$X^4$	X 
TCR profiling		X 					X 	X 	X 

- 1 A formalin-fixed paraffin-embedded (FFPE) tumor tissue sample (for e.g., immunohistochemistry, tumor mutational burden) must be obtained from each patient from the latest available archival tumor tissue. If such tissue cannot be provided, the sponsor approval of enrollment is needed. Details regarding the preparation of slides and number of slides to be prepared will be described in the lab manual.
- 2 An optional fresh tumor biopsy (aspirates are not acceptable), which is collected before Cycle 1 Day 1, preferably derived from advanced stage disease. This biopsy needs to contain tumor tissue and is taken after failure/stop of last prior treatment at screening or before first administration of BNT411. Additionally, biopsies should be collected at Week 6 ([+7 days], i.e., after 2 cycles of BNT411) and at disease progression or treatment discontinuation if it is considered feasible without a risk of complications for the patient. If deemed necessary by the investigator, the patient may be called in for an unscheduled visit, optional additional tumor biopsies may be collected if patients have unscheduled biopsies or tumor tissue resection during the course of the trial. Details to the preparation of fresh tumor biopsies will be described in the lab manual.
- 3 Cytokine samples will be taken at the same time points given for PK sampling with the exception of "end of infusion"—please refer to Table 1-4. Furthermore, cytokine samples will be taken at disease progression or treatment discontinuation. If an adverse event (AE) of cytokine release syndrome (CRS) is suspected, cytokines should be obtained at an unscheduled visit to confirm diagnosis.
- 4 Immune phenotyping samples are requested at D1 (pre-dose) and at D3 i.e. 48 hours (±2 hours) after start of infusion of BNT411 in Cycles 1 and 2. Furthermore, immune phenotyping samples will be taken pre-dose in Cycles 1 and 2 at Day 8 and Day 15 and pre-dose (D1) for every second cycle starting from Cycle 3 (e.g. Cycle 3, 5, 7, etc.) including time of disease progression or treatment discontinuation. Samples can also be taken at an unscheduled visit.

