As BNT411 was developed to release cytokines such as IFN $\alpha$  at an EC50 range lower than the EC50 required for release of cytokines such as TNF $\alpha$ , IL-6, and IL-10, the sponsor gauges the risk of higher grade clinically relevant and unmanageable manifestations of elevated cytokines as low and this protocol addresses the probability of such risks with a risk management plan. Upon stimulation, it has been described for TLR7 agonists that lymphocytes egress to the periphery and return within 24 to 48 hours. This sequestration effect has been attributed to the secretion of IFN $\alpha$  (Perkins et al, 2012) and may present as transient lymphopenia due to redistribution rather than cytotoxicity. Frequent laboratory monitoring is planned to observe this expected effect.

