# 6.1.1 BNT411

In Part 1A, BNT411 will be administered using a 100 mL intravenous infusion on Days 1, 8 and 15 of each 3-week treatment cycle (21 days) of the first 4 cycles after all required procedures and assessments have been completed. In the following cycles thereafter, BNT411 will be administered every 3 weeks on Day 1 of each 3-week treatment cycle (21 days) after all required procedures and assessments have been completed.

In Part 1B, BNT411 will be administered using a 100 mL intravenous infusion on Days 2, 8 and 15 of each 3-week treatment cycle (21 days) of the first 4 cycles after all required procedures and assessments have been completed. In the following cycles thereafter, BNT411 will be administered every 3 weeks on Day 2 of each 3-week treatment cycle (21 days) after all required procedures and assessments have been completed.

In both Part 1A and Part 1B, patients will be administered BNT411 according to dose levels outlined in Table 4-2. BNT411 will be administered as a body weight-based dosing. A cap on dosing for patients weighing 120 kg and more will be implemented in the proposed clinical trial.

In Part 1B, for combination with atezolizumab and chemotherapy, the administration will be in the following order:

Day 1: Atezolizumab → Carboplatin → Etoposide

Day 2: **BNT411** → Etoposide

Day 3: Etoposide

For each dosing of BNT411 in Cycle 1, patients will remain in the treatment center and be closely monitored for immediate AEs for at least 6 hours. Hospitalization is required for the first 24 hours after the first BNT411 administration in Cycle 1 for clinical observation and PK sampling. Prolongation of the hospitalization beyond 24 hours may be performed at the investigator's discretion if deemed necessary based on potential risks related to the trial treatment and clinical status of the patient. For each subsequent dose of BNT411 in all cycles, patients will be monitored for at least 6 hours.

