Change from baseline: Unless and otherwise specified, will be calculated as follows:

Change from baseline = post-baseline assessment value – baseline assessment value.

If either the baseline or post-baseline assessment value is missing, the change from baseline is set to missing as well.

For the derivations of PK and PD data, see Section [8.6.1](#) and [8.6.2](#).

Duration (Other than “Trial Treatment Duration” defined in Section [8.5.1](#)) will be calculated as follows:

- Duration = last observation date – first observation date + 1.

For conversion of days to months or years the following rules will be applied:

- 1 month = 30.4375 days
- 1 year = 365.25 days

Trial Day and Treatment Day will be calculated for each trial part (1A and 1B) as follows:

- Trial day:
 - If assessment date < treatment start date then trial day = assessment date – treatment start date
 - If assessment date >= treatment start date then trial day = assessment date – treatment start date + 1
- Treatment Day = treatment date – date of first dose of BNT411 +1

That is, trial day 1 indicates the date of treatment initiation.

For BNT411, it is Cycle 1 Day 1 of Part 1A and Cycle 1 Day 2 of Part 1B. For atezolizumab, carboplatin and etoposide it is Cycle 1 Day 1 of Part 1B.

All trial data will be presented as collected in the eCRF/visit assigned in external data. No windowing of data for the purposes of assigning to a visit will occur.

Unscheduled assessments will be listed only and not included in summaries/analysis.

Handling missing data:

For the purposes of assigning treatment-emergent flag for adverse events (AEs), partial or missing AE dates will be handled as follows (trial treatment date is the earliest date of BNT411 in Part 1A and earliest date of atezolizumab, BNT411, carboplatin and etoposide in Part 1B).

- If the day of the month is missing, the onset day will be set to the first day of the month unless it is the same month and year as trial treatment. In this case, in order to conservatively report the event as treatment-emergent, the onset date will be assumed to be the first date of trial treatment.

- If the onset day and month are both missing, the day and month will be assumed to be January 1, unless the event occurred in the same year as the trial treatment. In this case, the event onset will be coded to the day and month of treatment in order to conservatively report the event as treatment-emergent.

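### Table 1-8 places the Part 1B Day 3 immune phenotyping sample 48 h after BNT411, but with BNT411 given on Day 2, Day 3 is 24 h, so draws at two times can be filed under one visit

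*Protocol*

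**What the plan says.** - **Dosing day.** Protocol 6.1.1 states: "In Part 1B, BNT411 will be administered using a 100 mL intravenous infusion on Days 2, 8 and 15 of each 3-week treatment cycle" for the first four cycles. The Synopsis and Table 1-2 agree. SAP 8.1 does too when it fixes the first treatment day: "For BNT411, it is Cycle 1 Day 1 of Part 1A and Cycle 1 Day 2 of Part 1B".
- **Phenotyping time, Part 1B.** Table 1-8 footnote 4 asks for a pre-dose sample on Day 1 and a post-dose sample "at D3 i.e. 48 hours (±2 hours) after start of infusion of BNT411", in Cycles 1 and 2. It adds pre-dose samples on Days 8 and 15 of those cycles. The visit-window row of the table shows 1 h under D3.
- **PK and ECG time, Part 1B.** Table 1-4 footnote b reads "Time window for the Day 3 sample in the dose escalation is 24 hours", with a tolerance of 1 h, counted from the start of the Day 2 infusion.
- **Phenotyping time, Part 1A.** Table 1-7 footnote 4 asks for two early post-dose samples: 24 h on Day 2 (±1 h) and 48 h on Day 3 (±2 h). BNT411 is given on Day 1 there.
- **Visit window.** Table 1-2 gives Day 3 of Cycles 1 and 2 a window of +2 days. Footnote 28 reserves it for cases where immune phenotyping makes it unavoidable.
- **Analysis.** SAP 8.1 presents data under the visit as collected, with no windowing. For PK and PD data it uses the actual sampling time. If that time is missing, the analyst may treat the value as missing or impute the nominal time. SAP 8.6.2 makes the PD and biomarker analyses conditional on there being enough data.

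**The concern.** Footnote 4 gives the sampling time twice, once as a day and once as hours, and under Part 1B dosing these are different times. A site that follows the day label draws at about 24 h. A site that follows the hours draws on Day 4. The instruction does not say which governs.

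The difference could matter biologically. In its account of TLR7 agonists, Protocol 2.3.1.1 says that "lymphocytes egress to the periphery and return within 24 to 48 hours". Samples at 24 h and 48 h may therefore catch different phases of a transient effect. If both were summarised under one Day 3 label, the change from baseline in peripheral immune cells would average over two phases. That change is a stated exploratory endpoint for Part 1.

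**Working it through.** No sample-size or error-rate calculation is involved. The check is day arithmetic on the stated schedule.

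**Formula.** Nominal hours since BNT411 = (sample day − BNT411 dosing day) × 24.

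**1. Try to reproduce the stated 48 h.**
- Part 1A, dosed on Day 1: (3 − 1) × 24 = 48 h. This agrees with Table 1-7.
- Part 1B, dosed on Day 2: (3 − 2) × 24 = 24 h. The stated 48 h is not reproduced.
- Part 1B, counted from Day 1 (atezolizumab, carboplatin, etoposide): (3 − 1) × 24 = 48 h. This would reproduce the figure, but the footnote counts from the BNT411 infusion.
- Day on which 48 h falls in Part 1B: 2 + 48/24 = Day 4.

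**2. Compare the windows.**

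| Source | Stated time | Window |
|---|---|---|
| Table 1-4 footnote b (PK and ECG) | 24 h ±1 h | 23–25 h |
| Table 1-8 footnote 4 (phenotyping) | 48 h ±2 h | 46–50 h |

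The gap is 46 − 25 = 21 h, so the windows do not overlap.

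**3. Could a 46 h draw still fall on calendar Day 3?** Day 3 ends 48 h after midnight at the start of Day 2. A draw at 46 h falls within it only if the infusion began by 02:00 on Day 2 (48 − 46 = 2 h). That is not a realistic clinic start.

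**4. Read Table 1-8 against Table 1-7.** In Part 1A the 1 h window belongs to the 24 h sample and the 2 h window to the 48 h sample. The 1 h shown under D3 in Table 1-8 therefore fits 24 h. Within Table 1-8, the D3 label and its window point to 24 h, and only the hours in footnote 4 point to 48 h.

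**5. Can both draws be filed as Day 3?** The +2-day window runs from Day 3 to Day 5 (3 + 2), so a Day 4 draw lies inside it. With no visit windowing in the SAP, it stays under the Day 3 label.

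**6. What does the SAP do with the sample?** A recorded actual time separates 24 h from 48 h. A missing time may be replaced by the nominal time, which for this visit could be read as either. The SAP's own Part 1B schedule (Appendix 4, Table 6) does not settle it, because it points to Protocol Table 1-7, the Part 1A biomarker table.

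**7. Extent.** There is one such sample per cycle in two cycles. At the planned 6 to 30 DLT-evaluable patients in Part 1B, that is 6 × 2 = 12 to 30 × 2 = 60 nominal draws. This assumes every patient reaches Cycle 2 and ignores backfill and replaced patients.

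**The case against.** The strongest reply is that this is a footnote slip in an optional exploratory assay, and that the analysis plan already copes with it. Much of that stands. Phenotyping is exploratory, SAP 8.6.2 does not commit to analysing it, and the actual-time rule in SAP 8.1 covers every sample with a recorded time. The SAP specifies no visit-based phenotyping table. The markers that Protocol 4.3 names as possibly guiding escalation are type-1 interferons and other cytokines; Table 1-8 footnote 3 ties cytokine sampling to Table 1-4, so it is not affected.

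A reader might also infer more than the documents support:

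- **That samples will be mixed.** Nothing shows sites drawing at different times, and the laboratory manual, which Protocol 8.10 cites for sample details, is not among the documents. The supportable statement is that they can be mixed.
- **That no sampling plan can satisfy both tables.** Table 1-4 governs PK and ECG. A 24 h PK draw and a separate 48 h phenotyping draw can coexist, the latter inside the +2-day window. The conflict is inside Table 1-8.
- **That Part 1B cannot be compared with Part 1A.** Part 1A collects both times, so a Part 1B sample of known timing has a counterpart at either.
- **That the only pre-dose sample is Day 1.** Days 8 and 15 also have pre-dose samples. Day 1 is the only one before the first BNT411 dose, which matches the baseline definition in Protocol 9.4.1 and SAP 8.1: the last value before any trial treatment.

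What the reply does not remove is that the sampling instruction is wrong as written, and that the one gap in the SAP rule, imputation of a nominal time, falls on the visit whose nominal time is ambiguous.

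**Conclusion.** The inconsistency is real and the arithmetic is exact: under Day 2 dosing, Day 3 is 24 h and 48 h is Day 4. The discrepancy is 24 h, against stated tolerances of 1 to 2 h, and it applies to the Part 1B post-dose phenotyping sample in Cycles 1 and 2.

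The consequence is limited. It can blur one exploratory pharmacodynamic endpoint if the two draw times are pooled under the Day 3 label or if missing times are imputed. DLT evaluation, MTD, PK parameters and cytokine timing are untouched. A reader might infer that the RP2D is materially weakened. Protocol 4.1.1.2 lists available pharmacodynamic data as only one of several considerations, and the SAP introduction says Part 2 is no longer applicable, so the documents do not support that.

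The conclusion assumes that Day 2 dosing in Part 1B is as intended, which both documents state consistently. How far draw times actually differed cannot be judged from the documents.

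**What to change.** 1. **Protocol.** Reconcile Table 1-8 footnote 4, the D3 label and 1 h window of that table, and the Table 1-2 Day 3 window with Day 2 dosing, so that one post-dose time and one tolerance are stated. The sponsor must say which time was intended. If it is 48 h, the column needs a Day 4 label and the matching window; if it is 24 h, the hours and tolerance in footnote 4 change.
2. **SAP.** In any analysis of Part 1B phenotyping, group samples by recorded hours since the start of the BNT411 infusion, not by visit label. The actual-time rule in SAP 8.1 already permits this. Add one sentence that the nominal time is not imputed for this visit and that a sample without a recorded time is left out of time-specific summaries. While editing, point the biomarker row of Appendix 4, Table 6 to Protocol Table 1-8.

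The cost is a footnote and window correction plus one or two lines in the SAP, with no extra sample or visit. The SAP sentence is useful even for samples already taken.

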#### 2 Introduction

# 2.1 Background

#### 2.1.1 Overview of the Disease

Cancer is the second leading cause of death globally and is expected to be responsible for an estimated 9.6 million deaths in 2018 (Center for Disease Control and Prevention 2017; International Agency for Research on Cancer 2017). Refinements in conventional therapies such as chemotherapy, radiotherapy, surgery, and targeted therapies and recent advances in immunotherapies have improved outcomes in patients with advanced cancers. However, many immunotherapy treatments have demonstrated efficacy in only a selected group of cancers (Ventola et al, 2017; Yang et al, 2015). There is an unmet medical need for more effective and less toxic therapies with cures remaining scarce in patients with advanced solid tumors.

Small cell lung cancer (SCLC) accounts for approximately 15% of bronchogenic carcinomas. At the time of diagnosis, approximately 30% of patients with SCLC will have tumors confined to the ipsilateral hemithorax, which can be safely encompassed within a radiation field. These patients are designated as having limited-stage disease (LS-SCLC) (Murray et al, 1993). Patients with tumors beyond the ipsilateral hemithorax, including malignant pleural or pericardial effusion or hematogenous metastases are said to have extensive-stage disease (ES-SCLC).

SCLC is more responsive to chemotherapy and radiation therapy than other cell types of lung cancer; however, a cure is difficult to achieve because SCLC has a greater tendency to be widely disseminated by the time of diagnosis and to recur. ES-SCLC was chosen as the indication to escalate the doses of BNT411 with atezolizumab, carboplatin and etoposide.

#### 2.1.1.1 Incidence and Mortality

The overall incidence of SCLC in the United States and in the United Kingdom has decreased during the past few decades (Govindan et al, 2006; Riaz et al, 2012). The following table shows the estimated number of new cases of lung cancer and deaths from lung cancer (SCLC and non-small cell lung cancer [NSCLC] combined) in the United States in 2018 (American Cancer Society 2019) and in Europe in 2012 (Ferlay et al, 2013).

Lung Cancer	United States, 2018	Europe, 2012
New Cases	234,030	410,000
Deaths	154,050	353,000

Separate worldwide data for SCLC are not available. The incidence of lung cancer started to decline among men in the early 1980s and has continued to do so over the past 20 years. In contrast, the incidence in women started to increase in the late 1970s and did not begin to decline until the mid-2000s (American Cancer Society 2019; Siegel et al., 2019).

#### 2.1.1.2 Clinical Features

Lung cancer may present with symptoms or be found incidentally on chest imaging. Symptoms and signs may result from the location of the primary local invasion or compression of adjacent thoracic structures, distant metastases or paraneoplastic phenomena. The most common symptoms at presentation are worsening cough, shortness of breath and dyspnea. Symptoms from distant metastases may also be present and include neurological defect or personality change from brain metastases or pain from bone metastases. Infrequently, patients with SCLC may present with symptoms and signs of the paraneoplastic syndromes.

### 2.1.1.3 Diagnosis

Treatment options for patients are determined by histology, stage, and general health and comorbidities of the patient. Investigations of patients with suspected SCLC focus on confirming the diagnosis and determining the extent of the disease. The procedures used to determine the presence of cancer include the following: history, physical examination, routine laboratory evaluations, chest X-ray, chest computed tomography (CT) scan with infusion of contrast material and biopsy.

Before a patient begins lung cancer treatment, an experienced lung cancer pathologist must review the pathologic material. This is critical because SCLC, which responds well to chemotherapy and is generally not treated surgically, can be confused on microscopic examination with NSCLC (Travis et al, 1999).

## 2.1.1.4 Prognosis and Survival

Regardless of stage, the current prognosis for patients with SCLC is unsatisfactory despite improvements in diagnosis and therapy made during the past 25 years. Without treatment, SCLC has the most aggressive clinical course of any type of pulmonary tumor, with median survival from diagnosis of only 2 months to 4 months. About 10% of the total population of SCLC patients remain free of disease during the 2 years from the start of therapy, which is the time period during which most relapses occur. Even these patients, however, are at risk of dying from lung cancer (both small and non-small cell types) (Johnson et al, 1990). The overall survival (OS) at 5 years is 5% to 10% (Fry et al, 1996; Johnson et al, 1990; Lassen et al, 1995; Murray et al, 1993).

An important prognostic factor for SCLC is the extent of disease. Patients with LS-SCLC have a better prognosis than patients with ES-SCLC. For patients with LS-SCLC, median survival of 16 months to 24 months and 5-year survival of 14% with current forms of treatment have been reported (Fry et al, 1996; Janne et al, 2002; Murray et al, 1993; Turrisi et al, 1999). In patients with ES-SCLC, median survival of 6 months to 12 months is reported with currently available therapy, but long-term disease-free survival is rare. Prophylactic cranial radiation prevents central nervous system recurrence and can improve survival in patients with good performance status who have had a complete response or a very good partial response to chemoradiation in LS-SCLC or chemotherapy in ES-SCLC (Auperin et al, 1999; Slotman et al, 2007).

